To compare the incidence of treatment-emergent complications a logistic regression model will be used. Stratification factors will be added to the model. A similar model will be applied for all-cause mortality, the incidence of antibiotic treatment, number (proportion) of subjects needing extended treatment, number (proportion) of subjects requiring re-hospitalization, and number (proportion) of subjects not hospitalized at Day 6. The duration of antibiotic treatment will be analyzed analogously to the total length of hospitalization.

Time to viral negativity by qRT-PCR and viral culture will be analyzed analogously to that of time from start of study drug to hospital discharge. The viral load over time will be analyzed using mixed-effects modeling. Stratification factors will be added to the model and additional predictive baseline factors, including but not limited to baseline viral load, baseline resistance parameters and influenza A subtype, may be added.

The hospital recovery scale outcome on each separate day from Days 2 to 14 (excluding the primary time point) will be analyzed similarly to the primary endpoint. The day with 30% of subjects not hospitalized will be identified, and the results on that numeric day (eg, Day 5 or Day 6, etc.) will be reported.

Time to clinical response and time to respiratory response will be analyzed analogously to time from start of study drug to hospital discharge. Clinical response is defined as achieving 4 of the 5 following vital signs resolution criteria, including at least the fever and oxygen saturation criteria, maintained for at least 24 hours:

- having no fever (without the use of antipyretics within 8 hours),
- oxygen saturation of at least 94% without oxygen supplementation or return to pre-influenza infection oxygen saturation (in patients with a known pre-influenza oxygen saturation level <94%),
- improved respiratory status (a respiratory rate ≤ 24 breaths per min without supplemental oxygen or return to pre-influenza infection supplemental oxygen requirement in patients with chronic oxygen use),
- heart rate 100 beats per min or lower,
- systolic blood pressure of 90 mmHg or higher without inotropic support given within 2 hours of assessment.

Respiratory response is defined as achieving the following 2 criteria for at least 24 hours:

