- If the p-value is $> 5\%$, stop further testing of the secondary endpoints, and make a claim on “Hospital recovery scale at Day 6”, “Incidence in post-baseline complications”, “Time from start of study drug to hospital discharge”, “Time from ICU admission to ICU discharge”, and “Time to return to daily activities”.

Step 5: Test the sixth secondary endpoint (“Rate of re-hospitalization”)

- If the p-value is $\leq 5\%$, make a claim on “Hospital recovery scale at Day 6”, “Incidence in post-baseline complications”, “Time from start of study drug to hospital discharge”, “Time

from ICU admission to ICU discharge”, “Time to return to daily activities”, “Time from start to end of mechanical ventilation”, and “Rate of re-hospitalization”.

- If the p-value is >5%, make a claim on “Hospital recovery scale at Day 6”, “Incidence in post-baseline complications”, “Time from start of study drug to hospital discharge”, “Time from ICU admission to ICU discharge”, “Time to return to daily activities”, and “Time from start to end of mechanical ventilation”.

For the primary endpoint, the results from the proportional odds model will be used in the hypothesis testing. If the proportional odds assumption would not hold on the treatment effect, the p-value from the van Elteren test will be used. For the secondary endpoints time from start of study drug to hospital discharge, time from ICU admission to ICU discharge, time to return to daily activities, and time from start to end of mechanical ventilation, the results of the Gehan-Wilcoxon test will be used in the hypothesis testing. For incidence in post-baseline complications and rate of re-hospitalization the results of the logistic regression will be used. For all these evaluations p-value combination tests will be used, as described below.

The final analysis on the ITT-i set (to support FDA marketing approval) and the final analysis on the OST subset (to support marketing authorization approval in EMA) will be performed independently, using a 5% two-sided significance level for each.

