5.2.3. Analysis Methods

A proportional odds model will be used as primary model to analyze the hospital recovery scale on Day 6, modeling the common odds ratio of improvement on the ordinal scale of active treatment versus placebo. The model will include treatment, hospital recovery scale category at baseline and the stratification factors (NEWS2 category at screening, type of baseline SOC, and time since onset of influenza symptoms). In a first step equal slopes (i.e. proportional odds) for the treatment effect only and unequal slopes for the other covariates, will be modeled. If this model does not fit a full

proportional odds model will be applied, i.e. implying proportional odds for all covariates in the model. The common odds ratio from the final model will be considered as the estimate of the treatment effect. The actual values of the stratification factors will be used for all models, not as randomized. The proportional odds model will be defined in such a way that a common odds ratio smaller than 1 indicates larger improvement in the pimodivir treatment group.

Graphical displays and tabulations will be provided showing the proportion of subjects per hospital recovery scale category and day. Also, shift tabulations will be provided of the baseline hospital recovery scale category versus the post-baseline hospital recovery scale category, per day.

The proportional odds assumption will be assessed by testing for parallel slopes for the treatment effect only.

In addition, each of 5 dichotomizations of the hospital recovery scale, ie,

- Not hospitalized, vs worse (ie, hospitalized)
- Non-ICU hospitalized without supplemental oxygen (or better), vs worse
- Non-ICU hospitalized with supplemental oxygen (or better), vs worse
- In the ICU without invasive mechanical ventilation (or better), vs worse
- Invasive mechanical ventilation (or better), vs worse (ie, died)

will be analyzed using a logistic regression model, including treatment, hospital recovery scale category at baseline and stratification factors.

The hospital recovery scale will also be analyzed using the Van Elteren test with strata defined by the stratification factors^[3, 6].

A table will be created showing the number (%) missing HRS values at day 6 overall and by reason: study discontinuation: due to COVID-19 and not due to COVID-19, discharged against medical advice prior to day 5 and subjects that have no confirmed influenza A.

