Incidence of treatment-emergent adjudicated influenza complications	
The incidence of treatment-emergent adjudicated influenza complications from first study drug intake until the end of the study will be categorized in a hierarchical fashion. The incidence will be presented for the overall category, for the subcategories and for each adjudicated complication within a subcategory.
 
The overall category will consist of any adjudicated complication.
 
The following subcategories are defined:
 
 • Pulmonary complications: 
 ○ respiratory failure, ○ primary viral pneumonia, ○ secondary bacterial pneumonia, ○ exacerbations of chronic underlying pulmonary diseases, ○ bronchitis ○ other complications • Extrapulmonary complications: 
 ○ Cardiovascular and cerebrovascular disease (eg, myocardial infarction, congestive heart failure, arrhythmia, stroke), ○ Muscular disorders (eg, myositis, rhabdomyolysis), ○ Central nervous system (CNS) involvement, ○ Acute exacerbation of chronic kidney disease, ○ Decompensation of previously controlled diabetes mellitus, ○ Other infections (eg, sinusitis, otitis) ○ Other complications • Pulmonary complications including sinusitis and otitis • Major / minor complications • Infectious / non-infectious complications 
The complications sinusitis and otitis are determined based on their MedDRA preferred terms as listed in Attachment 1, table 6, for the protocol terms ‘Sinus infection’ and ‘ear infection’ respectively. Only if those terms are judged to be complications by the adjudication committee they will be included for the endpoint ‘Pulmonary complications including sinusitis and otitis.’

Incidence of not being hospitalized on Day 6.	On Day 6 (relative day) subject is in the hospital at least a part of the day (‘Yes’) or the subject is not in the hospital during the whole day (‘No’).
Incidence of hospital readmission	Does the subject require hospital readmission after first discharge (The start date of the hospital readmission must be at least 1 day in between the end of the previous hospitalization)? Categories will be Yes (1) or No (0).

Incidence of all-cause mortality	
Did the subject die after first dose of study drug?
 
Categories will be Yes (1) or No (0).

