Bootstrapping with replacement, considering also the actual proportion of subjects in each stratum, will be used to obtain a 100% sample size 10001 times. The median (95% CI) time-to event will be derived from the 10001 bootstrapped samples.

Cox Proportional Hazard model

A stratified Cox proportional hazards model will be used adjusted for the stratification factors and for the time from admission to start of treatment (for the time to hospital discharge and time to hospital discharge readiness),. The hazard ratio for the comparison of pimodivir versus placebo will be reported together with the 95% confidence interval. A Log-log plot of survival will be added to check the proportional hazard assumption of the Cox proportional hazards model.

For the subgroup analyses the Log-Log plot of survival will be shown for each subgroup category separately.

Logistic regression model

A logistic regression model (Firth's penalized likelihood approach), with treatment group and stratification factors as fixed effects, will be used to analyze binary outcomes and to obtain the odds ratios (95% CI) for the comparison of pimodivir versus placebo.

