5.3.2.1. Clinical outcome

Time-to event parameters for clinical outcome

The time-to event parameters for clinical outcome will be analyzed as described above using a stratified Gehan-Wilcoxon test, a stratified log-rank test, a Kaplan-Meier analysis, an accelerated failure time model and a Cox proportional hazards model. The Gehan-Wilcoxon test is the primary analysis for time-to-event parameters. The Kaplan-Meier analysis will provide the primary estimation of time-to-event.

Duration parameters

Descriptive statistics of the duration parameters will be shown for all subjects that had the specific event. e.g. only subjects admitted to ICU will be included in the total time in ICU analysis.

Total length of hospitalization, total time in ICU, total duration of antibiotics, and total time on mechanical ventilation will be analyzed by using the Hodges-Lehman approach. Corresponding 95% CIs will be presented as well.

Incidence parameters

For each parameter the number and percentage of subjects in each category and subcategory will be tabulated and listed. All Subjects in the applicable analysis set will be counted for the denominator of the proportion.

The occurrence (yes/no) as described for the incidence parameters will be analyzed using logistic regression as described above (Section 5.3.2).

The occurrence (yes/no) of influenza complications will be analyzed using logistic regression as described above for the following categories:

- the overall influenza complications
- the pulmonary complications,
- the extrapulmonary complications
- the infectious complications
- the non-infectious complications
- the major complications
- the minor complications
- the pulmonary complications including sinusitis and otitis

Hospital recovery scale outcome and fundamental hospital recovery scale outcome on Day 2 to 14

This parameter will be analyzed analogous to the primary endpoint: hospital recovery scale outcome on Day 6, but then for Day 2 to 14 with Day 6 excluded for the HRS and including Day 6 for the fundamental HRS. The proportional odds model will be applied, and the proportional odds assumption will be tested for the treatment effect. The same 5 dichotomization of the HRS will be analyzed using a logistic regression model. Also, similarly as the primary endpoint the Van Elteren test will be provided in case the proportional odds assumption is not valid. The MI analysis will not be applied.

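### Adding pre-dose level of care (ICU or invasively ventilated versus ward) to the logistic test of influenza complications would be a cheap efficiency and consistency gain; the planned test is valid without it

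*SAP*

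**What the plan says.** SAP 5.3.2 sets one Firth penalised logistic model for binary endpoints, "with treatment group and stratification factors as fixed effects". SAP 5.3.2.1 sends all the yes/no incidence parameters to it. Those defined in SAP 5.3.1.1 include complications, hospital readmission, hospitalization on Day 6 and all-cause mortality. SAP 5.1.1 makes the model confirmatory for two of them: "For incidence in post-baseline complications and rate of re-hospitalization the results of the logistic regression will be used".

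The recovery scale is handled differently in SAP 5.2.3. For the primary proportional odds model, "The model will include treatment, hospital recovery scale category at baseline and the stratification factors". Each of the five dichotomizations "will be analyzed using a logistic regression model, including treatment, hospital recovery scale category at baseline and stratification factors".

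Protocol 11.4 draws the same line for these endpoints. For complications it says "Stratification factors will be added to the model. A similar model will be applied for all-cause mortality" and then lists the other binary endpoints. It asks for baseline recovery category only in the dichotomized models.

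Two definitions matter for the remedy. SAP 2.5 and Attachment 6 derive baseline recovery category over the whole screening/Day 1 visit, without regard to when the first dose was given. SAP 4.1 separately lists ICU status and mechanical ventilation at baseline.

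**The concern.** Protocol 3.2 treats severity and condition at entry as the strongest predictors of outcome. Whether a subject enters on the ward, in ICU or ventilated plausibly predicts complications, and the logistic model sees it only through a two-level NEWS2 factor. Omitting a strong predictor from a logistic model moves the odds ratio towards 1, can cost power, and leaves chance imbalance in entry status unadjusted.

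Complications share Step 2 of the testing order with time to discharge. Steps 3 to 5 open only if both succeed, so lost power there also closes later endpoints.

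The SAP does not follow a rule of stratification factors only. It adds time from admission to treatment in the accelerated failure time and Cox models for discharge, and baseline viral load or titer for viral negativity. Two closely related Day 6 outcomes, hospitalized or not, are fitted with baseline recovery category in 5.2.3 and without it in 5.3.2. No reason is given for the difference.

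**Working it through.** **1. The plan's own figure.** SAP 1.4 gives a placebo distribution of 30/30/25/5/5/5% and a 38% reduction in the common odds ratio (OR 0.62). The treated distribution is then 40.9/29.9/19.4/3.4/3.3/3.2%. Whitehead's formula is N = 12(z₀.₉₇₅ + z₀.₉₀)² / {(ln OR)²(1 − Σp̄³)}, where p̄ is the mean category proportion. This gives 12 × 10.507 / (0.2285 × 0.9174) = 601, with power 89.9% at N = 600. The stated 600 is reproduced, but it concerns the primary endpoint only. The documents give no power for the binary endpoints.

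**2. What NEWS2 captures.** The strata are 4–5 and 6 or more. Under the substitutions in SAP 7.6.1, an invasively ventilated subject scores at least 3 (saturation) + 2 (oxygen) + 3 (consciousness) = 8. A ward subject on oxygen with saturation of 91% or less and respiratory rate 21–24 scores 3 + 2 + 2 = 7. Both fall in the upper stratum, so the model cannot separate them.

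**3. Chance imbalance.** Assume 20% are in ICU or ventilated at entry. Under simple randomization the SD of the between-arm difference is √(0.2 × 0.8 × 4/n): 3.3 points at n = 600, 4.6 at 300 and 6.5 at 150. An interim at 300–450 of 600 leaves 150–300 subjects in the second stage. Stratifying by NEWS2 reduces this only in part.

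**4. Single-fit simulation.** Firth models with Wald tests, N = 600, 1,200 trials per setting, both models fitted to the same trials. The Monte Carlo SE is at most √(0.25/1200) = 1.4 points.
- From the documents: complication rates of 15.6% (placebo, Phase 2b hospital study) and 23.8% (its placebo subgroup treated within 96 hours); OR 0.62, borrowed from the primary endpoint; 5% mortality, the Day 6 placebo assumption.
- Assumed: baseline categories 2–5 at 5/75/13/7%; 8% re-hospitalization; NEWS2 odds ratio 1.5, correlated with category; 85% on antivirals; 25% in the 72–96 hour stratum.
- Assumed odds by category, relative to category 3: weak 1/1/1.5/2, moderate 0.8/1/2.5/5, strong 0.5/1/5/15.

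Power (%) at two-sided 5%, without → with baseline category:

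| Endpoint (control rate) | Weak | Moderate | Strong |
|---|---|---|---|
| Complications (15.6%) | 46.2 → 46.7 | 45.0 → 46.3 | 38.8 → 44.4 |
| Complications (23.8%) | 61.2 → 61.1 | 58.3 → 60.5 | 49.7 → 54.7 |
| Re-hospitalization (8%) | 27.8 → 28.4 | 26.5 → 25.0 | 23.7 → 25.3 |
| Mortality (5%) | 18.9 → 20.4 | 18.2 → 19.8 | 15.8 → 17.3 |

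At the 2.5% level, which applies first under Holm, the complications results are of the same order:
- At 15.6%: 33.9 → 34.1, 34.2 → 35.8 and 29.3 → 33.5.
- At 23.8%: 49.8 → 49.5, 47.2 → 51.2 and 37.9 → 44.5.

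In the strong setting at 15.6%, the mean estimated odds ratio is 0.66 without the covariate and 0.61 with it. Under the null for complications, two-sided error was 3.6–5.9% without and 3.9–5.6% with.

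**5. Combination-test simulation.** SAP 5.1.2 combines separate pre- and post-interim p-values by the inverse normal method. With stages of 450 and 150, the weights are √(450/600) = 0.866 and √(150/600) = 0.5. Settings were 15.6% complications, OR 0.5 and one pooled ICU-or-ventilated indicator. Power without → with the indicator was 73.9 → 74.0% (weak), 69.5 → 71.8% (moderate) and 60.0 → 65.7% (strong). One-sided type I error was 2.2–2.5% throughout.

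**The case against.** The strongest reply is that this is a preference among valid analyses. Much of it stands:
- **Pre-specification.** Protocol 11.4 and SAP 5.3.2 name the same covariates for these endpoints. A reader might infer that the SAP departs from the protocol; it does not.
- **Validity.** A reader might take the odds ratio nearer 1 as bias. It is non-collapsibility: the two models estimate different odds ratios, and error control holds for both.
- **Covariates follow the outcome.** Recovery outcomes adjust for baseline recovery, and viral outcomes for baseline viral load. This is coherent but incomplete, since time from admission is not a baseline value of time to discharge.
- **The existing variable is unsuitable.** Complications count from first intake, while the SAP's baseline recovery category can include post-dose hours of Day 1. Carrying it over from 5.2.3 could adjust away early events that belong to the outcome. This stands and determines the remedy.
- **Size depends on assumptions.** With odds rising four-fold per category, or 4³ = 64-fold from category 2 to 5, simulated power went from 63.6% to 72.1% (15.6% complications, OR 0.5). A reader might quote that gain of about 8 points, but nothing in the documents supports such a gradient.

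One part does not stand: that a small second stage cannot carry another covariate. With a control rate of 15.6% and OR 0.5, the treated rate is 8.5% and the average 12.0%, so 150 subjects give about 18 events. Even so, the pooled indicator held type I error and did not lower power.

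The two Day 6 outcomes are also not identical. The scale counts readiness for discharge, whereas the incidence endpoint counts physical presence. That does not explain the different adjustment.

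**Conclusion.** The point holds as a minor improvement. For complications the expected gain is about 0 to 2 power points if level of care adds weak or moderate prognostic information beyond NEWS2, and about 5 to 6 if it adds a lot. One moderate setting reached 4 points at the 2.5% level. For re-hospitalization and mortality the changes run from −1.5 to +1.6 points, close to simulation error, so a benefit there should not be claimed. Type I error is near nominal either way.

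The baseline mix and prognostic gradients are not in the documents, and the strong case implies a 30-fold range of odds (0.5 to 15). The combination test was simulated for complications at one stage split only. The argument for the change is its low cost and the consistency it brings, not a defect in the planned test.

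**What to change.** Before unblinding, add one baseline indicator to the Firth model in SAP 5.3.2 for influenza complications: ICU or invasive mechanical ventilation versus ward. For consistency, use it for the other incidence endpoints too. Define it from status before the first study drug intake, using the ICU and ventilation data already collected, and not from the baseline recovery category of SAP 2.5 and Attachment 6. The rule should say that only invasive ventilation counts, because SAP 5.3.1.1 groups invasive and non-invasive ventilation together elsewhere. If the sponsor prefers the present model, one sentence giving the reason would suffice.

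The cost is one extra parameter in each pre- and post-interim fit and a short derivation rule. No new data are needed, and neither the sample size nor the testing order changes.

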5.3.2.1. Clinical outcome

Time-to event parameters for clinical outcome

The time-to event parameters for clinical outcome will be analyzed as described above using a stratified Gehan-Wilcoxon test, a stratified log-rank test, a Kaplan-Meier analysis, an accelerated failure time model and a Cox proportional hazards model. The Gehan-Wilcoxon test is the primary analysis for time-to-event parameters. The Kaplan-Meier analysis will provide the primary estimation of time-to-event.

Duration parameters

Descriptive statistics of the duration parameters will be shown for all subjects that had the specific event. e.g. only subjects admitted to ICU will be included in the total time in ICU analysis.

Total length of hospitalization, total time in ICU, total duration of antibiotics, and total time on mechanical ventilation will be analyzed by using the Hodges-Lehman approach. Corresponding 95% CIs will be presented as well.

Incidence parameters

For each parameter the number and percentage of subjects in each category and subcategory will be tabulated and listed. All Subjects in the applicable analysis set will be counted for the denominator of the proportion.

The occurrence (yes/no) as described for the incidence parameters will be analyzed using logistic regression as described above (Section 5.3.2).

The occurrence (yes/no) of influenza complications will be analyzed using logistic regression as described above for the following categories:

- the overall influenza complications
- the pulmonary complications,
- the extrapulmonary complications
- the infectious complications
- the non-infectious complications
- the major complications
- the minor complications
- the pulmonary complications including sinusitis and otitis

Hospital recovery scale outcome and fundamental hospital recovery scale outcome on Day 2 to 14

This parameter will be analyzed analogous to the primary endpoint: hospital recovery scale outcome on Day 6, but then for Day 2 to 14 with Day 6 excluded for the HRS and including Day 6 for the fundamental HRS. The proportional odds model will be applied, and the proportional odds assumption will be tested for the treatment effect. The same 5 dichotomization of the HRS will be analyzed using a logistic regression model. Also, similarly as the primary endpoint the Van Elteren test will be provided in case the proportional odds assumption is not valid. The MI analysis will not be applied.

A tabulation will be made of the (fundamental) hospital recovery scale outcomes at each day (including Day 6), taking only non-missing values into account (i.e.: the percentages of the six categories per day should sum up to 100%). A second tabulation will be made of the hospital recovery scale outcomes at each day including a category for missing values. The first day with 30% of subjects not hospitalized will be identified. All Subjects in the applicable analysis set will be counted for the denominator of the calculation.

